APPENDIX 8. EASE OF SWITCHING MEDICATIONS SCALE

Ease of Switching Medications:

The process of switching to the new medication was:

- Extremely Easy, Not Difficult At All
- Easy
- Neither Easy nor Difficult
- Difficult
- Extremely Difficult, Not Easy At all

APPENDIX 9. FORCED PREFERENCE QUESTIONNAIRE

Thinking about your experience with Xyrem and XYWAV, which would you prefer to treat your narcolepsy?

- Xyrem
- XYWAV

Please state the main reason for your preference below:

[Free Text]

1. LIST OF ABBREVIATIONS

AE adverse event

ALB albumin

ALK-P alkaline phosphatase

ALT alanine aminotransferase
AST aspartate aminotransferase

BP blood pressure

bpm beats per minutes

BUN blood urea nitrogen

Ca Calcium

CBC complete blood count

CFR Code of Federal Regulations

CI confidence interval

Cl Chloride

CRF case report form

COVID-19 coronavirus disease 2019

C-SSRS Columbia Suicide Severity Rating Scale

CSR clinical study report

CTCAE common terminology criteria for adverse events

CTMS clinical trial management system

DBP diastolic blood pressure

DSM-5 Diagnostic and Statistical Manual of Mental Disorders, 5th Edition

E/D early discontinuation ECG electrocardiogram

eCRF electronic case report form
EDS excessive daytime sleepiness

EOSMS Ease of Switching Medications Scale

ESS Epworth Sleepiness Scale

ET end of treatment
EU European Union

FDA Food and Drug Administration
FPQ Forced Preference Questionnaire

FSH follicle-stimulating hormone

GCP Good Clinical Practice

HCG human chorionic gonadotropin

HR heart rate

ICF informed consent form

ICH International Council for Harmonisation

IRT interactive response technology

K Potassium

MedDRA Medical Dictionary for Regulatory Activities

Na Sodium

NCI National Cancer Institute

NT1 Narcolepsy Type 1

NVAS Nausea Visual Analog Scale

PE physical examination

PGIc Participant Global Impression of Change

PHQ-9 Participant Health Questionnaire-9

PK Pharmacokinetic

PR pulse rate

PT preferred term

SAE serious adverse event
SAP statistical analysis plan
SBP systolic blood pressure
SD standard deviation
SE standard error

SoA Schedule of Activities SOC System Organ Class

TEAE treatment-emergent adverse event

TSH thyroid stimulating hormone

US United States

WBC white blood cell count

WHO World Health Organization

2. MODIFICATION HISTORY

Version History for SAP:

Version	Date	Description	
V1.0	09 NOV 2022	Original SAP	
V1.1	12 DEC 2022	8	

3. INTRODUCTION

The purpose of this statistical analysis plan (SAP) is to describe in detail the statistical methodology and planned analyses to be conducted for Protocol JZP 258-401-00, "A Phase 4 Multicenter, Open-label, Single-arm Study of Safety, Tolerability, Effectiveness and Treatment Optimization in Participants Switching from Xyrem to XYWAV for the Treatment of Narcolepsy" for inclusion in the Clinical Study Report (CSR). The current version is based on Original Protocol dated 08Dec2020. Any additional analyses or deviation from the analyses outlined in this plan will be documented with rationale in the interim and/or final CSR.

4. STUDY OBJECTIVES AND ENDPOINTS

4.1. Study Objectives

4.1.1. Objective

The objective of this study is to describe the clinical experience of participants switching from Xyrem to XYWAV for the treatment of narcolepsy with or without cataplexy in terms of safety, tolerability, effectiveness, and treatment optimization.

4.1.2. Exploratory Objective

The exploratory objective of this study is to describe the ease of conversion and participant preference of XYWAV in participants with narcolepsy with or without cataplexy.

4.2. Study Endpoints

4.2.1. Key Endpoints

- Adverse Events and Serious Adverse Events
- Change in the Nausea Visual Analog Scale
- Change in weekly rate of cataplexy attacks (for Narcolepsy Type 1)
- Change in Epworth Sleepiness Scale to assess excessive daytime sleepiness
- Participant Global Impression of Change
- Time to optimized dose and regimen
- Number of changes from first dose and regimen to optimized dose and regimen
- Number of participants dosing fasted versus dosing without consideration of food
- Timing and characterization of meals relative to dosing

4.2.2. Exploratory Endpoints

- Ease of Switching Medications Scale
- Forced Preference Questionnaire

5. STUDY DESIGN

5.1. Summary of Study Design

Study JZP258-401 is an open-label, single-arm, interventional study that is intended to provide descriptive assessments of safety, tolerability, effectiveness and optimization of treatment during participant transition from Xyrem to XYWAV. The dosing information obtained in this trial may be used to support that XYWAV can be dosed with or without food. If warranted, the data obtained from this study would be included to support future label discussions with regulatory agencies.

The target study population is participants with narcolepsy, with or without cataplexy that have remained on a stable regimen of Xyrem for no less than 2 months prior to start of this study, at any prescribed dose (up to a maximum of 9 grams) taken once, twice, or thrice nightly and with no single dose exceeding 6 grams.

5.2. Study Treatment

All participants will continue to stay on stable Xyrem dose and regimen during screening and baseline periods. During the Open Label Conversion and Treatment Optimization period, participants will switch to XYWAV initially at the same dose (gram-per-gram) and regimen as Xyrem, then expand the dose and regimen upon optimization with or without food. The total duration of the study is expected to be approximately 17 months, with duration of individual participant participation around 3 to 3.5 months. The study (Figure 1) comprises the following phases:

Screening Period (Up to 30 days)

To be eligible for the study, all participants must have been titrated to a tolerable and effective dose and regimen of Xyrem (with or without concomitant anticataplectics or stimulants), which shall have remained stable for ≥ 2 months prior to entry into study. During the initial Screening period of up to 30 days, all participants will be evaluated for eligibility based on screening assessments, with the option to be rescreened once if the rescreening is approved by the Medical Monitor. Rescreening may occur following resolution of transient exclusionary conditions or stabilization of conditions that were exclusionary in the unstable state (eg, unstable hypothyroidism) and is permitted only with the permission of the Medical Monitor. Participants who are approved for rescreening must be re-consented if re-screening occurs more than 28 days after the first consent, in which case, a new participant identification number should be assigned, and all screening procedures should be repeated.

Baseline Period (2 weeks)

Following study entry, participants will remain on the same stable dose and regimen of Xyrem during a 2-week Baseline period. Baseline weekly rates of cataplectic attacks and ESS scores (as a measure of EDS) will be determined in this period, in addition to other baseline treatment and safety measures as outlined in Schedule of Activities (Protocol JZP258-401-00 Section 1.3).

Intervention (Open-Label Conversion and Treatment Optimization) Period (6 weeks)

[figure not shown]
During the Intervention (Open-Label Conversion and Treatment Optimization) period, participants on a stable dose and regimen of Xyrem will be switched to the same dose (gram-pergram) and regimen of the study intervention drug (XYWAV). Any concomitant anticataplectics or stimulants will be maintained as per their current dose and regimen throughout the study.

Once the investigator determines that a stable dose and regimen has been achieved, XYWAV may be taken with or without food. If needed, XYWAV may be titrated to an optimized dose and regimen based on efficacy and tolerability, under the advisement and instruction from the investigator, with the goal to end the period with ≥ 2 weeks of optimized therapy on XYWAV.

Safety Follow-up Period

Following the Intervention period, participants will return for a Safety Follow-up visit 2 weeks after the End of Treatment (ET) or Early Discontinuation (E/D). Following the ET or E/D, including during the Safety Follow-up period, it is understood and expected that investigators will determine the appropriate course of care with the participant, and may resume any prescribed medications that were discontinued prior or during the study. There is no plan to monitor participants beyond the 2-week Safety Follow-up period.

Figure 1 Overall Design of Study JZP258-401

^{*}Adjustment to achieve optimal clinical benefit, with adequate control of cataplexy and EDS while maintaining tolerability per investigator judgment.

Abbreviation: EDS = excessive daytime sleepiness; wks = weeks

5.3. Power and Sample Size Considerations

An estimated total of 100 participants will be enrolled into this single-arm study. This number is considered sufficient to meet the study objectives. A formal sample size calculation has not been performed and formal hypothesis testing is not planned for data in this study.

5.4. Randomization and Blinding

All participants who sign the informed consent form (ICF) will receive a participant number. The participant number identifies the participant for all study procedures that occur throughout the study. This number is unique and once assigned, cannot be reassigned to another study participant. Study JZP258-401 is an open-label, single-arm trial, and therefore will have no blinding. Treatment allocation for this study will occur centrally through the use of an interactive response technology (IRT).

5.5. Interim Analysis

Based on enrollment, an optional interim analysis may be conducted after approximately the first 25 participants and 50 participants respectively, have completed or prematurely terminated the study to provide an early understanding of the clinical experience of participants switching from Xyrem to XYWAV. This data may be presented externally. This process will occur with no pause in enrollment.

As formal hypothesis testing is not performed, no alpha adjustments will be made for any interim analyses.

A Data Monitoring Committee will not be used for this study.

6. ANALYSIS SETS

For purposes of analysis, the following populations are defined:

Table 1Analysis Set

Analysis Set	Description
All Screened	The All Screened Analysis Set will include all subjects who provided a signed informed consent for this study.
	This analysis set will be used to summarize the number of screened, screen failure and enrolled subjects.
Enrolled	All participants who sign the informed consent form and meeting all eligibility criteria for the study.
	This analysis set will be used to summarize participant disposition, major protocol deviations (as classified in CTMS), and inclusion/exclusion from the Safety Analysis Set, including reasons for exclusion from it.
Safety	The Safety Analysis Set will include all participants in the Enrolled Analysis set who take at least one dose of Xyrem after providing informed consent.
	This analysis set will be used for summaries of all endpoints, except those which only pertain to data captured during the Intervention Period.

Analysis Set	Description
XYWAV Safety	The XYWAV Safety Analysis Set will include all participants in the Safety Analysis Set who take at least one dose of XYWAV.
	This analysis set will be used for summaries of all endpoints which pertain to only data captured during the Intervention Period.
XYWAV Efficacy	The XYWAV Efficacy Analysis Set will include all participants in the XYWAV Safety Analysis Set who finish the course of study.
	This analysis set will be used for summaries of all endpoints which pertain to only data captured during the Intervention Period.

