1.3. Schedule of Activities (SoA)

Table 3 Schedule of Assessments

Procedure	Screening Period (Up to 30 days before Day 1)	Baseline Period	Intervention Period (Open Label Conversion and Treatment Optimization Period)		Discontinuation (E/D) ³	Safety Follow-up Period
			Conversion from Xyrem to XYWAV ¹	Treatment Optimization on XYWAV ²		
Visit (V) Number ⁴	V1	V2	V3	V4 Clinic Visit	V5, V6 Phone Call	V7 Clinic Visit
Visit Window +/- Day or End of Week (W)	Day -30 to -1	Day 1 + 1 day	Day 15 + 3 days	W3 + 3 days	W4, W5 + 3 days	W6 + 3 days
Informed Consent	X					W10 +3 days
Inclusion/Exclusion Criteria	X	X				
Demographics	X					
Medical History	X	X				
Physical Examination	X					
Vital Signs (BP, HR, body temperature, RR)	X	X	X	X	X	X
Comprehensive metabolic panel, hematology, UA, TSH	X					
Urine Drug Screen	X	X	X		X	X
Alcohol Screen	X	X	X		X	X
Serum Pregnancy Test	X					

Procedure	Screening Period (Up to 30 days before Day 1)	Baseline Period	Intervention Period (Open Label Conversion and Treatment Optimization Period)			Discontinuation (E/D) ³	Safety Follow-up Period
			Conversion from Xyrem to XYWAV ¹	Treatment Optimization on XYWAV ²	End of Treatment (ET) ³		
Visit (V) Number ⁴	V1	V2	V3	V4 Clinic Visit	V5, V6 Phone Call	V7 Clinic Visit	V8
Visit Window +/- Day or End of Week (W)	Day -30 to -1	Day 1	Day 15 + 1 day	W3 +3 days	W4, W5 +3 days	W6 +3 days	W8 +3 days
Electrocardiogram	X						
Cataplexy Frequency Diary; Assess control of cataplexy (Appendix 5)	X ⁵	X	X	X	X	X	X
Review/discuss participant diaries for completeness	X	X	X	X	X	X	X
Nausea Visual Analog Scale (Appendix 6)		X ⁶			X ⁶	X ⁶	
Epworth Sleepiness Scale; Assess control of EDS	X					X	X
Forced Preference Questionnaire (Appendix 9)						X	X
Ease of Switching Medications Scale (Appendix 8)						X	X

Procedure	Screening Period (Up to 30 days before Day 1)	Baseline Period Xyrem-Stable Dose and Regimen	Intervention Period (Open Label Conversion and Treatment Optimization Period)			Discontinuation (E/D) ³	Safety Follow-up Period
			Conversion from Xyrem to XYWAV ¹	Treatment Optimization on XYWAV ²	End of Treatment (ET) ³		
Visit (V) Number ⁴	V1	V2	V3	V4 Clinic Visit	V5, V6 Phone Call	V7 Clinic Visit	V8
Visit Window +/- Day or End of Week (W)	Day -30 to -1	Day 1	Day 15 + 1 day	W3 +3 days	W4, W5 +3 days	W6 +3 days	W8 +3 days
Participant Global Impression of Change						X	X
Columbia-Suicide Severity Rating Scale Screening (Baseline version)	X						
Participant Health Questionnaire-9	X						

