4.1. Overall Design

The open-label, single-arm, interventional design of Study JZP258-401 is intended to provide descriptive assessments of safety, tolerability, effectiveness and optimization of treatment during participant transition from Xyrem to XYWAV. The dosing information obtained in this trial may be used to support that XYWAV can be dosed with or without food. If warranted, the data obtained from this study would be included to support future label discussions with regulatory agencies.

The target study population is participants with narcolepsy, with or without cataplexy that have remained on a stable regimen of Xyrem for no less than 2 months prior to start of this study, at any prescribed dose (up to a maximum of 9 grams) taken once, twice, or thrice nightly and with no single dose exceeding 6 grams.

An estimated total of 100 eligible participants with narcolepsy will be enrolled into this single-arm study. The total duration of the study is expected to be approximately 17 months, with duration of individual subject participation around 3 to 3.5 months. The study comprises the following phases:

Screening Period (Up to 30 days)

To be eligible for the study, all participants must have been titrated to a tolerable and effective dose and regimen of Xyrem (with or without any concomitant anticitaplectics or stimulants), which shall have remained stable for \geq 2 months prior to entry into study. During the initial Screening period of up to 30 days, all participants will be evaluated for eligibility based on screening assessments ([Section 1.3](#)), with the option to rescreen once ([Section 5.4](#)).

Baseline Period (2 weeks)

Following study entry, participants will remain on same stable dose and regimen of Xyrem during a 2-week Baseline period. Baseline weekly rates of cataplectic attacks and ESS scores (as a measure of EDS) will be determined in this period, in addition to other baseline treatment and safety measures as outlined in SoA ([Section 1.3](#)).

Intervention (Open-Label Conversion and Treatment Optimization) Period (6 weeks)

During the Intervention (Open-Label Conversion and Treatment Optimization) period, participants on a stable dose and regimen of Xyrem will be switched to the same dose (gram-per-gram) and regimen of the study intervention drug (XYWAV). Any concomitant anticitaplectics or stimulants will be maintained as per their current dose and regimen throughout the study.

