8. STUDY ASSESSMENTS AND PROCEDURES

- Study procedures and their timing are summarized in the SoA ([Section 1.3](#)).
- Immediate safety concerns should be discussed with the sponsor's Medical Monitor immediately upon occurrence or awareness to determine if the participant should continue or discontinue study intervention.
- Adherence to the study design requirements, including those specified in the SoA is essential and required for study conduct. Changes in study visit schedules or missed visits that lead to missing study information, must capture the specific information that explains the basis of missing data.
- All screening evaluations must be completed and reviewed to confirm that potential participants meet all eligibility criteria. Screen failure reasons will be captured in the interactive response technology (IRT) system.
- After screening procedures have been completed and eligibility criteria have been confirmed, eligible participants will be provided with instructions on how to discontinue any excluded medications. Document that the investigator has determined that discontinuation is safe and medically appropriate, the Medical Monitor has approved, and the discontinuation is medically supervised.
- Diaries and Questionnaires will be in electronic format within a secure application uploaded to the subject's mobile phone or tablet computer device of choice for personal completion. Site personnel will be able to provide instruction for uploading, use, and completion of the electronic diaries (e-diaries) and electronic questionnaires (e-questionnaire). The application is secure with unique username and password for access.
- Lab analyte measures and ECGs will be read by qualified personnel at the site (eg, a physician)
- Repeat or unscheduled samples may be taken for safety reasons or for technical issues with the samples.

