9.3. Analysis Sets

For the purposes of analysis, the following analysis sets are defined:

Table 6. Study Analysis Sets

Participant Analysis Set	Description
Enrolled	The Enrolled Analysis Set will include all participants who provide informed consent for this study. This analysis set will be used to summarize participant disposition, major protocol deviations (as classified in CTMS), and inclusion/ exclusion from the Safety Analysis Set, including reasons for exclusion from it.
Safety	The Safety Analysis Set will include all participants in the Enrolled Analysis set who take at least one dose of Xyrem after providing informed consent. This analysis set will be used for summaries of all endpoints.

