7.6. Changes to Planned Analyses

The changes in planned analyses between the protocol and SAP are the following:

- All Screened Analysis Set, XYWAV Safety Analysis Set and XYWAV Efficacy Analysis set are added in addition to the analysis sets defined in protocol section 9.3. Exclude potential screen failures from Enrolled Analysis Set defined in protocol section 9.3.
- National Cancer Institute (NCI) common terminology criteria for adverse events (CTCAE) version 5.0 or higher is added as the reference for AE severity classification.

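### SAP Table 1 nests both safety sets inside an Enrolled set conditional on eligibility and does not expressly keep a dosed participant later found ineligible in the AE incidence tables (minor)

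*SAP*

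**What the plan says.** Protocol 9.3 sets Enrolled by consent alone: "The Enrolled Analysis Set will include all participants who provide informed consent for this study". Its Safety set is the Enrolled participants who take Xyrem after consent.

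SAP section 6, Table 1, adds an eligibility condition. Enrolled becomes "All participants who sign the informed consent form and meeting all eligibility criteria for the study", with no statement of when eligibility is judged. The next two sets are built on it:

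- Safety: "The Safety Analysis Set will include all participants in the Enrolled Analysis set who take at least one dose of Xyrem" after consent.
- XYWAV Safety: "The XYWAV Safety Analysis Set will include all participants in the Safety Analysis Set who take at least one dose of XYWAV".

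SAP 10.2 bases the Xyrem-emergent AE summaries on Safety and the TEAE summaries on XYWAV Safety. SAP 8.2 and 8.6 put the disposition and deviation summaries on Enrolled. SAP 7.6 records the change and gives its aim: "Exclude potential screen failures from Enrolled Analysis Set defined in protocol section 9.3".

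**The concern.** A safety denominator should follow exposure. Here membership of both safety sets passes through an eligibility test that carries no time point. Suppose an entry breach comes to light only after dosing, for example an exclusionary history discovered at monitoring. On the words of Table 1 that person does not belong to Enrolled, and so belongs to neither safety set.

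The events at stake are those reported while the person was taking Xyrem or XYWAV in the study. Describing safety and tolerability is part of the study's main objective. SAP 5.1 says the data may support label discussions, and SAP 5.5 allows interim results from about 25 and 50 participants to be presented externally, where a single event carries more weight. The effectiveness, ease-of-switching and preference summaries in SAP 9 also depend on XYWAV Safety or a subset of it.

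**Working it through.** **Step 1. Trace the sets.** By Table 1, XYWAV Safety lies within Safety, and Safety lies within Enrolled, which requires consent and satisfaction of every eligibility criterion. For a consented participant who took both drugs but breached an entry criterion:

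| Set | Protocol 9.3 | SAP Table 1, literal | SAP Table 1, entry-check reading |
|---|---|---|---|
| Enrolled | in | out | in |
| Safety (Xyrem-emergent AE tables) | in | out | in |
| XYWAV Safety (TEAE tables) | not defined | out | in |

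**Step 2. Look for a passage that settles it.** Several passages favour the entry-check reading:

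- Protocol 4.1, on the Screening Period: "all participants will be evaluated for eligibility based on screening assessments".
- Protocol 8: "All screening evaluations must be completed and reviewed to confirm that potential participants meet all eligibility criteria".
- Protocol 1.3: the row "Inclusion/Exclusion Criteria" is marked only at Screening and Visit 2.
- SAP 7.6 limits the stated purpose to screen failures.

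None of these says what happens to a dosed participant whose breach is found afterwards. Table 1 also sits awkwardly with its own uses. If Enrolled holds only people who meet every criterion, a breach of a criterion can never appear in the deviation summary based on Enrolled. The tabulation of reasons for exclusion from Safety could not show the person either. That is good evidence of the intent, and it also shows that the words do not express it.

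**Step 3. Size.** The plan has no figure to reproduce: 100 is the planned enrolment without a formal calculation (SAP 5.3), and 25 and 50 are the approximate interim sizes (SAP 5.5). The number later found ineligible, k, is not given. The following is illustration only. It assumes that all 100, 50 or 25 were dosed with XYWAV.

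*One SAE in the study, in the one removed participant (k = 1):*
- Planned size: 1/100 = 1.0% becomes 0/99 = 0%.
- Second interim: 1/50 = 2.0% becomes 0/49 = 0%.
- First interim: 1/25 = 4.0% becomes 0/24 = 0%.

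*A common TEAE, assumed 30/100 = 30.0%:*
- k = 1: 29/99 = 29.3% if the person had the event, 30/99 = 30.3% if not.
- k = 5: 25/95 = 26.3% if all five had it, 30/95 = 31.6% if none did.

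*Upper bound when no event is seen.* The exact one-sided 95% limit is 1 − 0.05^(1/n). It gives 2.95% for n = 100, 2.98% for n = 99 and 3.10% for n = 95.

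*Chance of losing an event.* If x of 100 participants have an SAE and k are removed at random, the chance that at least one of the x is removed is 1 − C(100−x, k)/C(100, k). For x = 2 this is 2.0% at k = 1 and 9.8% at k = 5.

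Rates and bounds barely move. What can change visibly is whether a rare event appears in the table at all.

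**The case against.** The best reply is that the context already fixes the meaning:

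- The All Screened row of Table 1 is used to count screened, screen-failed and enrolled people, so failing screening and being enrolled are the two outcomes of screening.
- Protocol 5 speaks of departures from the enrolment criteria as protocol deviations, and SAP 8.6 summarises deviations on Enrolled.
- Protocol 7.1 deals with a positive drug screen or pregnancy test during the study by discontinuation. SAP 8.2 tabulates discontinuation reasons on Enrolled, so such people must still be in it.
- SAP 8.2 commits to accounting for everyone who consented. The AE and deviation listings in SAP 10.2 and 8.6 name no analysis set.

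All of this stands as evidence of intent, and it is why the point is minor. It does not close the gap. Protocol 7.1 concerns events arising after entry, not an entry breach discovered late. A listing does not put an event back into an incidence table.

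A reader might infer three stronger things that the documents do not support.

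1. *That eligibility cannot be decided at entry*, because inclusion criteria 3 and 4 mention stable concomitant treatment throughout the study and contraception until after the last dose. SAP 8.2 tabulates still-ongoing participants on Enrolled at interim analyses, so membership must be known before treatment ends. The sentence in criterion 3 describes how the switch is carried out. These criteria add nothing to the point.
2. *That a treated participant can become a screen failure*, because protocol 5.4 states no dosing exception. The rest of that section describes minimal data collection and possible rescreening, which fits people stopped at screening.
3. *That the SAP means to drop dosed participants, or that their events would vanish from the report.* SAP 7.6 and the unrestricted listings point the other way.

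**Conclusion.** The point holds as a minor correction. Applied literally, Table 1 takes a dosed participant with a late-discovered entry breach out of the Xyrem-emergent AE and TEAE tables, which the protocol's consent-only definition would not have done. The likely intent was to remove screen failures only. That aim is sensible: candidates already take Xyrem, so under the protocol's definition someone who failed screening could still enter the Safety set.

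The effect is unknown and probably small. It is nil if the entry-check reading is programmed or if no such participant occurs. The figures above rest on an assumed number removed and, for the SAE example, on the further assumption that the removed person had the only event. They show what could be lost, not what is expected.

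**What to change.** In SAP Table 1:

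- **Enrolled:** participants who consented, passed the entry eligibility check and entered the Baseline Period at Visit 2, regardless of any ineligibility found later.
- **Safety:** Enrolled participants with at least one dose of Xyrem after consent.
- **XYWAV Safety:** everyone who took at least one dose of XYWAV, regardless of any ineligibility found later.

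Record the change in SAP 7.6. Screen failures are still removed, and a late-found breach can then appear in the deviation summary.

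The cost is a few lines of SAP text, with no new data or analyses. AE figures may shift slightly in either direction, or not at all if this reading was already intended.
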